1 INTRODUCTION

1.1 BACKGROUND

Bipolar disorder (BD) is a major chronic mental health condition, with a lifetime risk of 1-2%. It primarily affects mood and energy/activity levels. People with BD have episodes of depression where they feel very low and lethargic, and episodes of mania where they feel very high and overactive. Each episode can last for several weeks or longer, and the pattern of mood swings varies widely between individuals. The global burden of this disease, measured in disability-adjusted life years (one DALY represents the loss of the equivalent of one year of full health), rose by 14.9% over the period 2005-15 (GBD 2015 DALYs and HALE Collaborators, 2016). In 2015 BD ranked 21st among 310 diseases studied in terms of global years of life lost from disability (GBD 2015 Disease and Injury Incidence and Prevalence Collaborators, 2016). It usually begins in early adulthood and thus accounts for significant economic loss in all societies.

BD is a heritable disorder and stressful life events or physical illness can trigger the onset of the illness. The main pathophysiology is poorly understood and current treatment and prevention strategies are suboptimal (and many medications for BD have significant side effects). There is consequently a need to identify effective new interventions for clinical use.

In recent years, case studies have demonstrated the benefit of the ketogenic diet (KD; low-carbohydrate and high-fat) in psychiatric conditions. In a 2013 small case series of BD, patients reported significant mood stabilisation on a KD, exceeding that from medication. A 2019 case series documented complete resolution of symptoms in 2 people with schizophrenia, a condition significantly overlapping BD, where similar changes in metabolism are observed (increased pyruvate and lactate). In 2019, 165 self-reports of those adhering to the KD from online BD forums were analysed, 56% reported remission of symptoms or significant mood stabilisation and a further 29% reported some degree of mood stabilisation. This survey demonstrated that the diet is being used in the online BD community. Some psychiatrists are now recommending the KD as a treatment adjunct in their clinical practice. Several recent reviews have concluded that there is now some evidence of KD having beneficial effects on many of the major features of BD, including: reduction of oxidative stress, improved mitochondrial function and biogenesis, improved glutamate/GABA transmission and reductions of intracellular sodium and calcium. Calls for clinical trials have been made.

A novel hypothesis on the mechanism underlying BD has been described by our group and others, including how the KD may counter this. There is substantial evidence of impaired use of glucose in the mitochondria (parts of all human cells responsible for energy production) in people with BD. These developments have been paralleled by advances in understanding the metabolic component to mood disorders, as recently summarised by Brietzke (2018). Problems with glucose metabolism are relatively common in people with BD, as demonstrated by an increased frequency of type 2 diabetes, metabolic syndrome, and insulin resistance. Other conditions caused by problems with glucose metabolism, such as Polycystic Ovary Syndrome, are also associated with an increased frequency of BD.

We have described in detail a novel hypothesis on the mechanism by which hyperinsulinaemia disrupts the production of energy by mitochondria in the brain,

resulting in increased levels of specific biomarkers, including lactate and pyruvate. We reference our recent publications (Campbell 2019, 2020) on this topic and have attached a paper currently submitted for publication (Campbell 2021) which reviews this in detail. Higher levels of these metabolites have been described in BD compared to the general population and may be linked to mood instability. The KD can provide an alternative energy source to glucose (ketones) that can bypass this abnormal processing of energy and allow for more stable levels of energy production.

The KD has been established as a safe and effective therapy for seizure reduction in epilepsy through a Cochrane review of randomized controlled trials and almost a century of clinical use. NHS ketogenic diet services run throughout the UK, and there is potential to build on this experience. The diet's most significant biological effect is that it induces the state of "ketosis" wherein mitochondria in the body and brain preferentially oxidise fatty acids (ketones) instead of glucose. This metabolic shift reduces seizures by 50% in around 50% of subjects (Martin 2016). It is thought that this is due to ketones providing an alternate fuel source to dysfunctional mitochondria which cannot effectively use glucose for energy. In this respect, the underlying disease process may be similar to BD (there are many parallels between the clinical presentations of BD and epilepsy, and several medications are effective in both conditions). Several clinical trials have also trialled use of the KD for other conditions and, in general, relatively low levels of negative side effects are reported (although this has not yet been explored in BD).

The only clinical trial of the KD in BD registered in clinicaltrials.gov is a small pilot study [n=20] from Stanford University looking at a subgroup of both BD and schizophrenia patients who are overweight or obese. In comparison, our research proposal will only look at BD patients, and weight will not impact on our inclusion criteria. In addition to metabolic and psychiatric outcomes, we will also conduct brain imaging.

1.2 RATIONALE

If shown to be effective, the use of the KD to treat BD has the potential to open up a new treatment approach, which could be used alongside established treatments, and potentially reduce the number of medications patients need to take (as well as reduce the overall costs to health, community and society). Reducing the number of medications would reduce risks associated with polypharmacy, and negative side effects, and patients would have greater control over managing their illness. In addition, new insights on the metabolic component of BD may help reduce morbidity and mortality from obesity, diabetes and coronary heart disease.

It is important that an adequately powered and carefully designed randomised controlled trial is conducted to assess the above hypotheses and explore whether the KD results in improved mood stability in this population. There are no previous such trials. Together with an understanding of any negative effects of the KD in BD patients, this would help inform the increasing use of KD by significant numbers of individual patients and in an increasing number of clinical practices. If shown to be ineffective this will help direct research away from KD into other promising new interventions for BD. Prior to running a full clinical trial, it is vital that a pilot study is undertaken to assess the acceptability and feasibility of the KD intervention, including the level of support required for participants. This will allow us to understand how to introduce and maintain the diet effectively, investigate adherence rates and adverse effects of the KD in people with BD, and carry out detailed assessments as they would be performed in a future trial.

2 RESEARCH QUESTIONS

2.1 PRIMARY RESEARCH QUESTION

This pilot study aims to understand the feasibility and acceptability of a low-carbohydrate, high-fat ketogenic diet (KD) in 25 patients with bipolar disorder (BD) who are euthymic at time of presentation. This will also test the acceptability of data capture instruments, explore rates of compliance, adverse effects, the range and variability of outcome parameters (to inform a future clinical trial design), the level of support required to introduce the KD successfully in this population, and the most appropriate diet formulation and means of introduction and maintenance. The effect of a KD on the frequency and severity of mood instability, quality of life, and functional outcomes will be investigated. This feasibility work will help us to develop a protocol for a future clinical trial.

2.2 SECONDARY RESEARCH QUESTION

The study also aims to better understand the proposed mechanism of action of the ketogenic diet by investigating biochemical and more detailed metabolic evidence (through blood tests and brain imaging), and the relationship between these biomarkers and clinical outcome. Definitive conclusions will not be drawn due to the small sample size.

2.3 PRIMARY OBJECTIVES

- Recruit 25 patients with bipolar disorder [BD] who are euthymic at time of presentation.
- Support the introduction of a KD over an 8-week period and determine the most appropriate diet formulation and means of introduction and maintenance in this group.
- Investigate adherence rates with a KD intervention in this patient group and the level of support required to introduce KD successfully.
- Investigate evidence of short-term metabolic changes [from blood metabolomic and brain imaging studies] associated with KD consistent with underlying study hypothesis for mechanism of action.
- Report any adverse effects associated with use of KD in this patient group.
- Explore the feasibility and acceptability of the KD to patients and clinicians.
- Explore feasibility and acceptability of study processes for a future trial e.g. recruitment procedures, monitoring and outcome assessments.
- Document the range and variability of outcome parameter values (to inform future clinical trial design).
- Investigate preliminary signals of efficacy on mood instability, quality of life and functional outcomes in this patient cohort (in a before-after assessment).

2.4 SECONDARY OBJECTIVES

 Investigate biochemical and more detailed metabolic (metabolomic and CNS magnetic resonance imaging) evidence for the proposed mechanisms of KD action outlined in the study hypothesis and relationship between these biomarkers.

- Work collaboratively with and communicate results to diverse academic, policy, public and patient groups through multiple channels.
- Work with Bipolar Scotland and other patient groups at all stages of the research process from study design to interpretation and communication of results and appropriate translation of findings into patient care.

2.5 PRIMARY OUTCOME MEASURES

There is not a single primary outcome as this is a pilot study investigating the feasibility and acceptability of an intervention and gathering data on a range of other parameters as noted above. Therefore, all outcomes are equally important, and it will be essential for us to understand how to make all aspects of the study workable for a subsequent trial.

- Timeline estimates for future trial recruitment by measuring the number of interested participants and fully recruited participants from each avenue of recruitment during the estimated 4-month recruitment period
- Participant level of compliance with dietary interventions measured using fidelity checklists at weeks 0, 2, 4, 6, and 8, and daily ketone measurements during the 8-week intervention period
- Participant level of compliance with study assessments as recorded on the case report form at baseline and week 8
- Participant level of compliance with continuous study assessments measured using data from the study devices and apps (actigraph device, ketomojo device and app, and ilumivu app) or that sent directly to the research team by participants, during the 10-week study period
- Quality of life measured using the EQ5D-5L at baseline and week 8
 Productivity and activity impairment measured using the Work Productivity and Activity Impairment Questionnaire at baseline and week 8
- Participant resource use measured using a Within Trial Resource Use Questionnaire at baseline and week 8
- Staff time and cost in delivering dietary interventions, measured by keeping contemporaneous records throughout the 10-week study period
- Attrition rate measured using the number of participants who consent to participate who remain in the study until the end of follow-up at 10 weeks, to help inform estimation of sample size for a future trial
- Acceptability and experience of the study participants evaluated via telephone interviews after the main study has ended as part of a process evaluation

2.6 SECONDARY OUTCOME MEASURES

- Mood stability measured by the Affective Lability Scale (ALS18) and Beck Depression Inventory (BDI) at baseline and at 8-week followupHypomania/mania symptoms measured using the Young Mania Rating Scale (YMRS) at baseline and 8-week follow up
- Glucose/ketone ratio measured using ketomojo devices daily throughout the 10 week study period
- Identification of specific metabolic changes in glucose, ketones and TCA metabolites associated with the KD that are predicted by the study

- hypothesis, measured using serum and brain MRI measures at baseline and week 8
- Mood, energy, speed of thought, impulsivity and anxiety measured using visual analogue scales from 1-100 at daily ecological momentary assessments during the 10-week study period
- Episodes of bipolar depression and hypomania/mania occurring during the study period assessed by repeat MINI Neuropsychiatric assessment at baseline and week 8.
- Sleep duration and circadian activity/rest rhythmicity parameters assessed by actigraphs throughout the 10-week period (to include 2 weeks of stepping down the diet).

3 STUDY DESIGN AND METHODS

3.1 STUDY SETTING

Recruitment and subsequent face-to-face contacts will take place in the Department of Psychiatry (University of Edinburgh), and the Clinical Research Facility (CRF) and imaging department at the Royal Infirmary of Edinburgh (RIE). Participants will also have regular phone contact with members of the research team. They may have additional phone contact with the University of Glasgow if they decide to take part in semi-structed interviews as part of the process evaluation.

3.2 TYPE AND LENGTH OF STUDY

This is a pilot study which is estimated to last 12 months. Individual participants will be involved for 10-12 weeks.

3.3 KETOGENIC DIET INTERVENTION

All study participants will receive a low-carbohydrate, high-fat ketogenic diet intervention for an 8-week period, the first 2 weeks of which will be an adaptation period. The 8 weeks will then be followed by a 2-week cessation period. They will continue usual medical treatment from their regular care teams, including mental health services.

Based on the successful experience of the study dietitians in administering the KD to adults with epilepsy, we will identify a KD formulation associated with good levels of adherence. We will work closely with Patient and Public Involvement (PPI) representatives from Bipolar Scotland to develop and refine materials to support patients in adopting this diet.

Participants will have an initial meeting with a dietitian, lasting up to 2 hours, to discuss the details of the diet, food preferences, monitoring, and potential risks. They will request that participants complete a food diary to bring to their first appointment, to help plan what meals may be most appropriate for them to try on a KD. This will involve recording everything they eat and drink for 3 days prior to attending. International guidelines for the management of adults treated with ketogenic diet therapies (Mackenzie 2021) suggests that 'preparation and training must be individualised to provide the greatest likelihood of success', and we will endeavour to make this is a key part of our dietary initiation.

The diet will be gradually introduced over a 2-week period. Support will be via dietary supervision over the first few days to check adherence to prescribed diets, problem solve and identify any adverse effects, which will mainly occur over the phone or via email. Dietitians will provide guidance and practical support around establishing and characterising the diet, using recipe cards and planning, dietary booklets and providing advice on common problems. We will have support from a Professor of Behavioural Science to develop our approach to behavioural aspects of the intervention including barrier identification, problem solving, habit formation, social support, reducing negative emotions, and restructuring the environment.

The majority of contact with the dietitian will be by phone or email to reduce the burden on participants, but with the option of face-to-face appointments if needed. After initiation of the diet, contact will be weekly. A dietitian will be contactable during normal working hours and will aim to respond within 48 hours. Experience has shown that it takes 2-3 weeks to establish the diet. There will be a 2-week cessation period after 8 weeks on the diet whereby participants are supervised to gradually step down from the ketogenic diet, unless they chose to continue it.

Possible side effects associated with commencing the KD include fatigue, thirst, irritability, hunger, and altered bowel habits (particularly constipation) (Mackenzie 2021). Participants will be informed of these, and simple strategies to manage them. Other common side effects include, weight loss, hyperlipidaemia, leg cramps, menstrual irregularity (in women of childbearing age), nausea, and vomiting. Common side effects are typically mild and can often be managed with diet adjustments under the guidance of a dietitian or nutritionist and infrequently require medical intervention. Smaller meals, increased plant fibre intake, restriction of processed fat sources, exercise, and increased sodium and fluid intake can often prevent or alleviate common symptoms such as constipation (Mackenzie 2021). These strategies will be implemented in this pilot study if required. We will also introduce the diet slowly over a period of 2 weeks which reduces the chances of these side effects being experienced.

As the Ketogenic diet is high fat it may increase blood levels of cholesterol and triglycerides. These levels will be monitored before and after starting the diet. We will minimise this adverse effect of the diet by using unsaturated fats where possible. High levels of cholesterol and triglycerides usually return to normal when the diet is weaned. We will also introduce the diet slowly over a period of 2 weeks which reduces the chances of side effects being experienced.

In line with the international recommendations mentioned above (Mackenzie 2021), we will advise participants to increase their fluid consumption and take a multivitamin and mineral supplement that meets recommended daily allowances. Participants will only follow the diet for 8 weeks (plus a 2-week cessation period) during the pilot study and so the chances of deficiencies if they do not choose to take these is low. If they chose to continue to follow the diet, we will recommend they continue the multivitamin.

The dietitians will have a written protocol detailing what to do in specific situations, e.g. if participants glucose is too low or ketones too high. Participants will be encouraged to contact the dietitian if they have any concerns. It will be communicated both verbally and in written form by the dietitian to participants what adverse effects they may experience and how to manage these. Participants will be asked to notify the research team of any adverse effects they experience via email to allow the team to respond in a timely manner. .

If participants are unable to manage to prepare their own meals, we will consider providing pre-prepared meals on a case-by-case basis. We will also consider providing pre-prepared ketogenic meals for a 2-week period for all participants at the beginning of the study to support them when initiating the diet. Our main aim is to ensure participants achieve ketosis, and the methodology may need to be adapted within the pilot study to ensure we are enabling participants to do this.

In addition to support from the dietitian, participants will have the contact details of a psychiatrist on the research team, who will be available during normal working hours to answer any questions they may have about other aspects of the study, or if they have concerns about their mental state.

We will complete a focus group with patients to inform the refinement of the intervention.

3.4 PARTICIPANT EVALUATION (see appendix 1 and 2 for study flowchart and participant flow infographic)

Participants will be advised not to provide their personal details when completing any free text questions as part of the study questionnaires and/or during telephone interviews.

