3.7 PROCESS EVALUATION

The process evaluation will explore the feasibility and acceptability of both the intervention, and elements of the study design, and it will be conducted following the Medical Research Council guidelines (Moore 2015). The process evaluation will assess: (i) intervention elements, i.e. acceptability, context, fidelity, exposure, and (ii) study related elements, i.e. acceptability of recruitment processes, outcome measures and contamination. It will also develop and refine the programme theory.

Quantitative process data will include adherence to the diet, measured via the finger prick blood tests to see if ketosis has been achieved. The dietitian will also complete weekly fidelity assessment of intervention delivery by the dietitians, using a fidelity checklist at the weekly update, which could be over the phone or via email. This will measure the extent to which the KD was delivered as intended.

Semi-structured telephone interviews will take place with 15 patients and 5 staff after the ten- week intervention period is complete and will take 40-60 minutes. Participants will be approached by telephone about taking part, and if they agree they will be sent an information sheet and consent form. At the interview the consent form will then be reviewed, and an audio recording of their consent to take part will be made and stored separately from the interview data. Patients will be purposively sampled to include a range gender, age, socioeconomic status and engagement with the intervention. Staff will be sampled to include dietitians from both centres and other health professionals including psychiatrists. Interviews will explore the acceptability of the evaluation methods and intervention; impact of the intervention; barriers and facilitators, contamination, suggestions for improvements as well as contextual factors influencing intervention impact. Interviews will be audio recorded on encrypted devices (to AES256 standard or above) and transcribed verbatim.

Qualitative data will be analysed using thematic analysis. Quantitative data will be analysed descriptively.

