4 STUDY POPULATION

4.1 NUMBER OF PARTICIPANTS

This study will aim to recruit 25 patients meeting the study criteria and consenting to take part.

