10 STATISTICS AND DATA ANALYSIS

10.1 SAMPLE SIZE CALCULATION

No formal sample size was calculated as this is a small feasibility study. We are not planning to draw firm conclusions about the efficacy of the diet.

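### Symptomatic adverse effects of the diet have no scheduled enquiry, no dedicated pre-diet rating and no listed CRF item, although reporting them is a primary objective

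*Protocol*

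**What the plan says.** Section 2.3 lists as a primary objective: "Report any adverse effects associated with use of KD in this patient group".

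The Protocol touches on how such effects come to light in several places:

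- **Start of the diet (Section 3.3):** "Support will be via dietary supervision over the first few days to check adherence to prescribed diets, problem solve and identify any adverse effects".
- **Afterwards (Section 3.3):** "After initiation of the diet, contact will be weekly". No adverse-effect question is attached to this contact. The only instrument named for it is the fidelity checklist in Section 3.7, described thus: "This will measure the extent to which the KD was delivered as intended".
- **Participant reports (Section 3.3):** "Participants will be asked to notify the research team of any adverse effects they experience via email". The stated purpose is that the team can respond quickly.
- **Follow-up visit (Section 3.4.2):** bloods, imaging, questionnaires and physical measures are repeated. No adverse-effect enquiry is listed.
- **General statements:** Section 3.8 includes the identification of adverse effects in the supervision to be costed. Section 11.2 sets the window from consent to the end of follow-up.
- **Recording:** Section 11.3 places adverse events in the CRF as part of the outcome measures, without a separate form.

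Section 3.3 also names what to expect: "Possible side effects associated with commencing the KD include fatigue, thirst, irritability, hunger, and altered bowel habits". It goes on to list weight loss, raised lipids, leg cramps, menstrual irregularity, nausea and vomiting.

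**The concern.** In a single-arm pilot, what can be said about side effects depends on how they were asked about and what they are compared with. Here there is no control group, so the participant's own pre-diet state is the only comparator.

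For bodily symptoms the Protocol fixes neither part. After the first days, whether a mild symptom is recorded depends, on the routes spelled out, on the participant deciding to write an email. Willingness to do so plausibly varies with mood and engagement. In addition, some listed effects, notably fatigue and irritability, can be part of bipolar disorder itself. Section 11.3 tells the investigator not to record events that fit the expected course of the underlying disease. Without a pre-diet rating there is little to anchor that judgement.

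At stake is the side-effect profile that the pilot hands on to the future trial. An analysis plan cannot repair this later: symptoms that were not asked about cannot be analysed, and a pre-diet rating cannot be obtained once the diet has started.

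**Working it through.** **Step 1. Is there a figure in the plan to reproduce?** No. The Protocol states no expected frequency of adverse effects and no capture proportion. On size it says "This study will aim to recruit 25 patients meeting the study criteria and consenting to take part" (Section 4.1) and "No formal sample size was calculated as this is a small feasibility study" (Section 10.1).

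**Step 2. Set the sections side by side for a symptomatic effect such as constipation in week 5.**

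| Element needed | What the Protocol gives |
|---|---|
| Scheduled question | None stated at weekly contact (3.3, 3.7) or follow-up (3.4.2) |
| Route spelled out | Participant email (3.3) |
| Time window | Consent to end of follow-up (11.2), no method |
| Place in the CRF | Required by 11.3; no adverse-event item in the lists in 8 and 8.2 |
| Place among outcomes | 11.3 treats adverse events as part of the outcome measures; none is listed in 2.5 or 2.6 |
| Severity grade | Required for serious adverse reactions only (11.4.3) |
| Pre-diet rating | None described for the listed symptoms |

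Section 11.6 bases quarterly safety reports on the CRF, so the missing item affects those too.

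**Step 3. What does have a baseline?** Biochemistry including lipids, weight, blood pressure, the mood scales and the MINI are done before and on the diet, and medical history is on the CRF. The gap concerns symptoms. The daily ratings in Section 3.4.1 cover energy but not bowel habit, thirst, hunger, cramps or nausea. The 10 weeks they span equal 8 weeks of diet plus 2 of cessation, so no pre-diet run-in is specified.

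**Step 4. What could incomplete capture do at n = 25?** All inputs except n are assumptions. Let p be the true proportion affected and c the chance that an affected participant's effect is recorded.

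Expected number recorded = 25 × p × c. Probability that none is recorded = (1 − p × c)^25.

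| p | c | Expected number recorded | Probability of none |
|---|---|---|---|
| 10% | 100% | 2.5 | 7.2% |
| 10% | 75% | 1.88 | 14.2% |
| 10% | 50% | 1.25 | 27.7% |
| 10% | 25% | 0.62 | 53.1% |
| 20% | 100% | 5.0 | 0.4% |
| 20% | 50% | 2.5 | 7.2% |
| 20% | 25% | 1.25 | 27.7% |

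For example, with p = 10% and c = 50%: (1 − 0.05)^25 = 0.277.

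**Step 5. What could the missing baseline do?** Assume that a symptom is present before the diet in 20%, persists, and newly appears in 10% of the rest. On the diet it is present in 0.20 + 0.80 × 0.10 = 28%, or 7 of 25. Only 0.80 × 0.10 = 8%, or 2 of 25, are new. If every recorded report were taken as a diet effect, the count would be 7 × c against a true 2. It is too high when c exceeds 2/7 = 29% and too low below that. The sign of the error therefore depends on a capture proportion that nobody knows.

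**The case against.** The strongest defence is that email is not the only route.

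- Saying that early supervision identifies adverse effects does not say that identification then stops. Section 3.8 describes dietary and psychiatric supervision as including it, without limiting it to the first days. Section 11.2 covers the whole period from consent, and a psychiatrist sees each participant at follow-up.
- The fidelity checklist is a process-evaluation tool and is not said to be the whole content of the weekly contact.
- Email is presented as a way to get a quick response.
- The CRF itself, the fidelity checklist and the dietitians' written protocol are not at hand and might contain the questions. So might the pre-diet nutrition history mentioned in Section 5.1.

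Much of this stands, and it rules out four stronger readings that a reader might infer:

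1. *Adverse effects are found only by email, or actively sought only in the first days.* Sections 3.8, 11.2 and 11.3 say otherwise. What is missing is the method.
2. *A primary objective to estimate a rate will be missed.* Section 2.3 asks for adverse effects to be reported. Section 2.1 attaches the word rates to compliance.
3. *Nothing is compared with the pre-diet state.* Laboratory values, weight, blood pressure and mood scales are. Section 11.3 also counts a pre-existing condition only if it has unexpectedly worsened.
4. *The reported frequency will be too low.* Step 5 of the working shows that it could err either way.

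What the defence does not supply is a question, a schedule or a listed field. Section 3.8 is a costing description and Section 11.2 a time window. The lists in Sections 8 and 8.2 still do not match Section 11.3. The unseen documents might close the gap, but the Protocol does not refer to them for this purpose.

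**Conclusion.** The point holds in a limited form. For symptomatic effects, the Protocol states an aim and a window but no solicited enquiry after the first few days, no dedicated pre-diet rating and no listed CRF item. Effects may be under-captured, or usual symptoms may be attributed to the diet. Neither the net direction nor the size can be derived from the document.

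The figures above rest on assumed incidence, capture and background prevalence, and on participants being independent. They show only that with 25 participants incomplete capture can matter: an effect with 10% incidence goes entirely unseen with probability 7.2% at full capture and 27.7% at half capture. Neither the sample size nor the descriptive character of the analysis is called into question. This is a cheap improvement worth making before the first participant starts the diet, because the baseline rating cannot be recovered afterwards.

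**What to change.** - Turn the side effects already listed in Section 3.3 into a one-page checklist, each item answered yes or no with a severity grade.
- Ask it once before the diet, at each weekly dietitian contact that already takes place, and at the follow-up visit in weeks 6 to 8.
- Add a matching field to the CRF, and name adverse effects in Sections 8 and 8.2 and in the outcome list, so that these agree with Section 11.3.
- Keep email for anything that arises between contacts.
- Report the number of participants with each symptom that is new or worse than before the diet, and show solicited and spontaneous reports separately.

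The cost is a one-page form and a few minutes per contact, with no extra visits or staff. The reported frequency will probably be higher than spontaneous reporting would give, so the report should state how effects were elicited.
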